HRP-503B – BIOMEDICAL RESEARCH PROTOCOL
(2017-1)

Protocol Title: Mechanisms for restoration of hypoglycemia awareness

Principal Investigator: [name], MD

Version Date: August 2, 2022

Clinicaltrials.gov Registration #: NCT03738852

SECTION I: RESEARCH PLAN

1. **Statement of Purpose:** State the scientific aim(s) of the study, or the hypotheses to be tested.

Aim 1: Determine the impact of frequent hypoglycemia and hypoglycemia unawareness on brain responses to visual food cues as well as brain functional connectivity in T1DM patients.

Aim 2: Assess the impact of antecedent bouts of hypoglycemia on brain glucose transport/metabolism during hyperglycemia in T1DM Unaware, T1DM Aware as well as healthy controls using ¹H, ¹³C magnetic resonance spectroscopy (MRS).

Aim 3: Determine if reducing hypoglycemia and glycemic variability using a continuous glucose monitor (CGM) reverses altered brain glucose transport/metabolism and functional connectivity in hypoglycemia unaware T1DM patients.

Optional Sub Study: Assess the impact COVID-19 pandemic and related shutdown has had on the management of diabetes amongst patients with T1DM.
2. **Probable Duration of Project:** State the expected duration of the project, including all follow-up and data analysis activities.

5 years
3. **Background:** Describe the background information that led to the plan for this project. Provide references to support the expectation of obtaining useful scientific data.

The DCCT and EDIC trials established the benefits lowering blood glucose to “near normal” levels in type 1 diabetes (T1DM) patients ¹⁻³. This has led to the widespread use of more intensified insulin therapy to prevent or delay diabetes complications. However, global application of intensive insulin therapy has been limited by a higher rate of severe hypoglycemia, often occurring without warning symptoms and thus reducing the patient’s ability to take corrective action ⁴. As a result, many patients do not and/or become afraid to achieve target glycemic goals, since their immediate fear of hypoglycemia exceeds their fear of future long-term complications ^{5,6}. In non-diabetic subjects, hypoglycemia provokes a multi-tiered defense system including: 1) suppression of

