It is noteworthy in this regard, that both healthy human subjects rendered mildly hypoglycemic for several days and T1DM patients receiving intensive insulin therapy are able to maintain brain glucose uptake during acute hypoglycemia, whereas healthy controls show a 20-30% decrease ^{26,27}, suggesting that prior hypoglycemia exposure induces the human brain to more efficiently use glucose much like that seen in rodent studies ^{28,29}. Furthermore, organ balance studies found a larger fraction of glucose is non-oxidatively metabolized in intensively treated T1DM patients, suggesting an increased ability to use alternative fuels, e.g. monocarboxylic acids ³⁰. In keeping with this possibility it has been reported that brain acetate transport and metabolism are increased 2-fold in intensively treated T1DM patients ³¹, findings supported by our data showing upregulation of monocarboxylic acid transporter (MCT) gene expression in diabetic rats exposed to recurrent hypoglycemia ³². Thus, T1DM patients appear to adapt to antecedent hypoglycemia in part by developing both more efficient brain transport and oxidation of monocarboxylic acids. Use of alternative fuels for brain metabolism may be a useful protective hypoglycemia adaptation, but it might also alter proper awareness of a falling blood glucose since ATP generated by mitochondrial monocarboxylic acid oxidation is most effective in supplying energy for basic brain functions, but is less useful when rapid energy is needed to drive the glutamate-glutamine cycle for complex functions. This is better served by the quick energy supplied by anaerobic glycolysis, much like in an exercising muscle.

Recent studies using the hypoglycemic clamp and fMRI scanning in hypoglycemia unaware and aware T1DM patients and healthy controls have showed distinct differences in patterns of brain responses. In particular, T1DM patients who are aware of hypoglycemia (T1DM-Aware) have greater activity in sensory integration brain regions (e.g. parietal lobe and caudate nucleus) in response to hypoglycemia, whereas hypoglycemia unaware T1DM patients (T1DM-Unaware) show no detectable changes in brain reward regions during hypoglycemia. The underlying mechanisms behind these differences remain unclear. Thus, we believe it is important clinically to assess: 1) if these differences are driven purely by recurrent hypoglycemia or by other closely linked factors

[figure not shown]

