After 14 days of wearing the CGM, it will be removed by a trained study staff member. To remove the sensor, the adhesive patch will be gently peeled off from the skin, together with the sensor. Removal of the sensor is a painless procedure. The sensor will be discarded after use.

Note regarding order of visits: CGM placement will occur up to 14 days prior to the subject's first scan (fMRI or MRS). CGM removal will occur on the same day as the subject's first scan (fMRI or MRS). Due to the many complexities of scheduling, although the fMRI is part of Aim 1, the subject may have the MRS scan done first, which is part of Aim 2. The order of scans in no way effects subject safety or research integrity. T1DM subjects will have a second CGM placed after the first scan and will wear this CGM until the second scan, where it will be removed. Therefore, T1DM subjects will wear the CGM two times, once before each scan for up to 14 days prior.

4. fMRI Scan with hyperinsulinemic euglycemia-mild hypoglycemia clamp: All subjects will arrive on the morning of the scan at 7AM following an 8-hr fast. T1DM subjects will be instructed to continue their home insulin regimen until they arrive at the Yale Magnetic Resonance Research Center (MRRC) that is equipped with infusion rooms for IV and line placements. A urine pregnancy test will be performed on all women of childbearing potential, and women who are pregnant will be excluded. Following IV placements and baseline blood collections at ~8 AM subjects will receive an insulin infusion (2 mU/kg/min) together with a variable glucose infusion to keep glucose levels at ~100-110 mg/dl. Once glucose levels are stabilized outside the magnet (~45 min), they will be transferred into the MRI for a 2-step hyperinsulinemic euglycemic (90-100 mg/dl)-mild hypoglycemic (55-60 mg/dl) clamp. Initially, baseline structural scans will be obtained, followed by blood oxygen level dependent (BOLD) contrast acquisitions during visual cues and cognitive tasks. At each clamp step, participants will also be asked to complete questionnaires assessing hypoglycemia. Plasma glucose will be measured every 5-10 min. Throughout, blood will be obtained for insulin, glucagon, cortisol, catecholamines and other hormonal and metabolic blood tests. A1c will also be measured at this visit.

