- a. Food Cues: Picture stimuli for fMRI are high-calorie/high carbohydrate food, and non-food neutral pictures selected from Web sites and from the International Affective Picture System.
- b. Cognitive tasks: include tasks to assess working memory (N-Back), attention (Grad-CPT) and reward (Card guess) that have been adapted for the MRI setting. In order for these tasks to be as accurate as possible, the subjects will need to think that they will get a monetary bonus depending on how they do. In reality, all subjects will "win" and get this bonus.

Aim 2: The same 3 subject groups who participated in Aim 1 will participate in Aim 2. As previously stated, for ease of scheduling, this visit may precede the fMRI visit discussed above.

1. 1H-[13C] MRS scanning and Hyperglycemic Clamp: Participants will arrive at MRRC at 7AM on the morning of the study after an 8 hour overnight fast. A urine pregnancy test will be performed on all women of childbearing potential, and women who are pregnant will be excluded. Following IV placements and baseline blood collection, at ~8 AM all T1DM subjects will receive a low dose insulin infusion to prevent ketosis during the MRS study and a variable glucose infusion to keep plasma glucose levels at ~100-110 mg/dl. Once glucose levels are stabilized, the subjects will be transferred into the 4T

scanner (¹³C ¹H for POCE) for the hyperglycemia clamp with labeled glucose. At the start of the study, plasma glucose will be increased to ~180 mg/dl by a primed continuous infusion of 99% 1-¹³C glucose (Cambridge Isotope Lab) (dextrose 1.1 M) and will be maintained at ~180 mg/dl throughout the study with a variable infusion of 60% ¹³C glucose (dextrose 1.1 M). Plasma glucose will be measured every 5 min. Throughout, blood will be obtained for insulin, fructose, sorbitol, ¹³C enrichment and other hormonal and metabolic blood tests. A1c will also be measured at this visit. After tuning, calibration, and acquisition of scout images for anatomical localization, metabolite concentrations will be obtained from 18 ml³ voxel. Using metabolic modeling we will determine rates of glucose uptake, TCA cycle (VTCA) and glutamate/glutamine cycling (Vcycle) as well as measure absolute glucose and fructose levels and ¹³C labeling.

Aim 3: T1DM-UA subjects that completed Aims 1 and 2 will participate in Aim 3.

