4. Repeat brain MRS and fMRI scans: At 12 weeks, all subjects will repeat fMRI and MRS analyses of brain glucose transport/metabolism under hypo- and hyperglycemia exactly as described in Aims 1 and 2. At 12 weeks, the subjects in Group 2 will repeat fMRI and MRS analyses of brain glucose transport/metabolism under hypo- and hyperglycemia exactly as described in Aims 1 and 2. A1c will also be measured at all scan visits. Hypoglycemia questionnaires will also be repeated, in addition to repeat cognitive assessments (using different test versions to reduce practice effects).

Note regarding order of visits: As is the case in Aims 1 and 2, CGM placement will occur up to 14 days prior to the subject's first scan of Aim 3 (fMRI or MRS). CGM removal will occur on the same day as the subject's first scan of Aim 3 (fMRI or MRS). Due to the many complexities of scheduling, there is no order that the fMRI and MRS must be performed. The order of scans in no way effects subject safety or research integrity.

Optional Sub Study: Subjects from Aim 1 and 2 with T1DM: (1) hypoglycemia unaware (T1DM-UA) (N=40) and (2) hypoglycemia aware (T1DM-A) (N=25) will be given the opportunity to participate in this optional sub study. We will only contact those previously enrolled participants who agreed to be re-contacted for future research by indicating such on the AIM 1 and 2 consent form.

1. Consenting: Subjects will be consented for this optional Sub study through the Qualtrics study link. The consent form will be provided as a study question. Subject will either click yes or no to agreeing to completed issued questionnaires. If subject, clicks yes and provides name and date, questions from survey will be provided. If subject clicks no, subject will not be provided additional questionnaires.
2. Subject Contact: Only subjects with T1DM and already eligible to participate in Aim 1 and Aim 2 will be contacted via telephone and explained the purpose of the sub-study.
3. Diabetes and health status questionnaires: All participants who agree to participate will be asked to complete questionnaires (all standard, well-validated questionnaires) for assessing hypoglycemia, self-evaluate their diabetes healthcare, general stress and anxiety during the COVID-19 pandemic and unprecedented stay-at-home experience. Questionnaires include:
 - a. Clarke, Gold, Pedersen : Classifies awareness of hypoglycemia, three different measures

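### The claim that scan order cannot affect research integrity is unsupported: the fMRI visit induces hypoglycemia, the exposure Aim 2 studies, and the MRS analyses have no order term

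*Combined protocol and SAP*

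**What the plan says.** **How order is set.** In Section I, item 4 (Research Plan), the note on visit order under Aim 1 reads: "Due to the many complexities of scheduling, although the fMRI is part of Aim 1, the subject may have the MRS scan done first". The Aim 2 text repeats that "for ease of scheduling, this visit may precede the fMRI visit discussed above". The note under Aim 3 says of the week-12 scans that "there is no order that the fMRI and MRS must be performed". Both notes close with the assertion "The order of scans in no way effects subject safety or research integrity".

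**What the fMRI visit does.** It is a "2-step hyperinsulinemic euglycemic (90-100 mg/dl)-mild hypoglycemic (55-60 mg/dl) clamp", given to all three groups.

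**What Aim 2 studies.** Section I, item 1 states it as: "Assess the impact of antecedent bouts of hypoglycemia on brain glucose transport/metabolism during hyperglycemia". The MRS visit measures brain glucose at about 180 mg/dl. In item 3 (Background), studies of earlier hypoglycemia are read as "suggesting that prior hypoglycemia exposure induces the human brain to more efficiently use glucose".

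**How it is analysed.** Section I, item 13 gives the Aim 2 model as group, glycemic state, the interaction of the two, and a random subject effect. Neither order nor the interval between scans is a term. Item 13 has no Aim 3 analysis paragraph. Average brain glucose is a co-primary outcome.

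**The concern.** At one visit the protocol delivers an instance of the exposure whose effect it measures at the other. Whether that instance comes before or after the MRS measurement is left to the calendar. Nothing in the plan randomises or balances order, sets a minimum gap between the scans, or makes a subject's week-12 order match baseline.

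If one clamp leaves some effect on brain glucose at the MRS visit, there are two ways for it to enter the results:

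- **Aim 2:** the share of subjects scanned fMRI first differs between two groups, and part of the carry-over appears as a group difference.
- **Aim 3:** that share shifts between baseline and week 12, and part of the carry-over appears as change on the glucose monitor.

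An absolute statement that order does not matter therefore sits badly beside the plan's own rationale. It also removes the reason to prespecify any adjustment.

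**Working it through.** **Inputs from item 13.** Target difference in brain glucose 0.22; SD 0.26 (quoted there with a difference between low- and high-variability groups, used here as the between-subject SD); 25 Aware, 25 controls, 40 Unaware; Aim 2 significance level 0.01. Sidedness is not stated for the human aims, so two-sided is assumed. The mixed-model contrast is approximated by a two-group comparison.

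**The plan's own figure first.** Item 13 claims 80% power for 0.22 in Aim 2. For 25 v 40, SE = 0.26 × √(1/25 + 1/40) = 0.0663. The normal approximation gives Φ(0.22/0.0663 − 2.576) = 77.1%; the noncentral t with 63 df gives 74.4%. This is a little under 80%, but it is only the yardstick here.

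**Bias formula.** Let c be the carry-over of the clamp on MRS brain glucose, and p₁ and p₂ the shares scanned fMRI first in the two groups (or at the two time points). For a carry-over common to both, bias = c × (p₁ − p₂). The documents give neither c nor p, so the values below are assumptions: c at a quarter, a half and all of the 0.22 target, with a 20-point gap in shares. Rejection rates are from the noncentral t, 63 df, alpha 0.01.

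| Assumed c | Bias = c × 0.20 | Share of 0.22 | Bias/SE | Type I error | Power if bias opposes a true 0.22 |
|---|---|---|---|---|---|
| 0 | 0 | 0% | 0 | 1.0% | 74.4% |
| 0.055 | 0.011 | 5% | 0.17 | 1.1% | 68.9% |
| 0.11 | 0.022 | 10% | 0.33 | 1.4% | 63.0% |
| 0.22 | 0.044 | 20% | 0.66 | 2.7% | 50.4% |

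**How likely is a 20-point gap?** If order were a fair coin toss for every subject, an exact binomial calculation gives a gap of 20 points or more between 25 and 40 subjects 12.3% of the time.

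**If order is unrelated to group.** A common carry-over is then noise, not systematic bias. With a 50/50 mix it adds c²/4 to the variance. For c = 0.22 the SD becomes √(0.26² + 0.22²/4) = 0.282, and power (normal approximation) falls from 77.1% to 68.5%. For c = 0.055 it falls only to 76.6%. An order term recovers nearly all of this.

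**Aim 3.** The same formula applies to the MRS change, with p₁ and p₂ the fMRI-first shares at baseline and week 12. If every subject keeps the same order, p₁ = p₂ and the bias is zero for a carry-over that is equal at both times. No error rate is put on Aim 3, because the plan gives no SD of change and no analysis model.

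**Aim 1.** At baseline neither order places a study-induced hypoglycemia before the fMRI measurement. MRS first puts only a hyperglycemic clamp ahead of it.

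**The case against.** **The evidence for carry-over from one clamp is thin.** The Background finding concerns "both healthy human subjects rendered mildly hypoglycemic for several days" and intensively treated patients, and it concerns uptake during acute hypoglycemia. Aim 2 measures brain glucose at about 180 mg/dl after at most one study clamp. Unaware subjects already have a history of hypoglycemia, so one more bout may add little. This stands: carry-over is plausible, not shown, and could be nil. It does not supply the missing support for an absolute claim.

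**No mechanism ties order to group.** Final awareness class uses hormones and questionnaires from the fMRI visit (item 4, Aim 1), so a scheduler cannot know it when booking the first scan. This largely stands for Aware v Unaware. Controls, however, are known from the start, a provisional class is available from the questionnaires at sensor placement, and chance gaps remain. For Aim 3 nothing keeps the mix stable over time.

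**Stronger readings that the documents do not support.**

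- A reader might infer that the bias is large. The top assumed carry-over equals the whole 0.22 target, so one mild clamp would have to reproduce the full between-group difference.
- A reader might put the Aim 3 false-positive rate at about 17%. That needs a bias of 0.044, 36 pairs and an SD of change of 0.26. The plan's 0.26 is not an SD of change, and 36 pairs appears nowhere; the plan treats 40 as the number before its dropout allowance.
- A reader might say that an order effect could never be found. Sensors come off on scan days, so visit dates should show order and interval. What is missing is prespecification.
- A reader might count the second sensor worn only by T1DM subjects as a bias route. The study sensor is blinded, and nothing in the documents links it to brain glucose.

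**Conclusion.** The point holds for the MRS outcomes: the Aim 2 group contrasts and the MRS part of Aim 3. The integrity claim is unsupported and conflicts with the reason for doing Aim 2, and no design or model feature guards against an order effect.

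Whether there is bias, and how much, cannot be determined from the documents. It needs a carry-over from a single clamp together with an order mix that differs by group or over time, or else a carry-over that itself differs by group or over time. The illustrated range (bias 0.011-0.044, Aim 2 type I error 1.1%-2.7% against 1%) rests on an assumed carry-over of 0.055-0.22, an assumed 20-point imbalance, SD 0.26 and a two-sided test. Zero is also possible. This is a worthwhile low-cost safeguard, not a demonstrated flaw in the results.

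**What to change.** 1. Remove the research-integrity claim from the visit-order notes under Aims 1 and 3. The safety part of the sentence is not disputed here.
2. Keep each Aim 3 subject's week-12 scan order the same as at baseline.
3. Where scheduling allows, balance order between controls and T1DM subjects, and within T1DM by provisional awareness class from the questionnaires at sensor placement. The final class is not known in time.
4. Record order and interval between scans from the visit dates.
5. Add a prior-clamp indicator (fMRI before MRS in the same round: yes/no) to the Aim 2 MRS model and to the Aim 3 MRS analysis, which has still to be written. Enter the interval only for fMRI-first subjects; for MRS-first subjects it follows no clamp in that round, so a common interval term would be misspecified. In Aim 3 the indicator mainly serves subjects whose order could not be kept.
6. Report a group-by-order check, because a main-effect term does not remove a carry-over that differs by group, and a sensitivity analysis in MRS-first subjects. Label both descriptive. With half of each group, roughly 12 v 20, power for 0.22 at the 0.01 level is only about 35%.

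**Cost:** some scheduling freedom and one or two degrees of freedom, with no extra visits. If scanning is already complete, items 4 to 6 can still be done from visit dates, provided they are specified before the MRS data are analysed.

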1. Group Assignment: 40 T1DM-UA subjects will be assigned to use a Dexcom G6 continuous monitoring system for 8 to 12 weeks, until they reach stable glycemic variability measured by coefficient of variation (CV) Additional training sessions will be conducted as needed to ensure familiarity and comfort with system operation.
2. Continuous glucose monitoring (CGM): Dexcom G6 continuous glucose monitoring system (DexcomG6 Pro System) is a real time continuous glucose monitoring device indicated for the management of diabetes in persons age 2 years and older. Is factory calibrated so there is no need for calibrations. It replaces fingerstick blood glucose testing for diabetes treatment decisions. The real-time Dexcom G6 System provides glucose trends, several sequential readings over time and glucose excursions facilitating care plan adjustments. This device may also be used as a retrospective glucose-recording device indicated for assessing glycemic variability.

The CGM consists of a sensor that measures glucose levels from the interstitial tissue. The CGM includes an applicator with a build-in sensor, which is packaged in a sterile unopened package. The sensor has a plastic wire-like tip that is placed under the skin and continuously measures the glucose level. The sensor can be worn for up to 10 days. It also comes with a transmitter, which connects to the sensor wire and sends real-time readings wirelessly to a receiver.

3. Follow-up visits: Subjects will be instructed to share data remotely to the study team through Dexcom Clarity, a continuous glucose monitor management application run by Dexcom. A member of the study team (physician and/or advanced practice register nurse) will review the information on a weekly basis and will make changes to their diabetes management as needed. Study participants will have in-person check-in visits for history, exam, and review of any potential adverse clinical or device-related events, if needed.

A study team member will communicate directly with the participants and participant's health care providers as they join the study and throughout the study, and will inform them about relevant clinical findings on the CGM including time spent in hyperglycemia and new increase or extended periods of hypoglycemia

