Data analysis will be conducted in collaboration with [name] at the Yale Center for Analytic Sciences. For Aim 1, we will require 25 T1DM aware and 25 healthy controls to provide 80% power to detect differences of 0.013 between them and the T1DM-Unaware subjects at the Bonferroni corrected 0.017 significance level. This sample size will also provide 80% power at the 0.01 level of significance to detect a difference of 0.22 for average brain glucose for Aim 2. We will enroll 27 aware and 27 healthy controls to accommodate a potential

5% inadequate scan rate. The T1DM Unaware group sample size (n=40) was first determined to provide sufficient power for Aim 3. T1DM Aware and healthy control sample sizes were then estimated based on power for aims 1 and 2. Our preliminary data shows differences in the co-primary outcome of average brain glucose between those with a low glucose variability index and those with a high glucose variability index of 0.455 (SD=0.26). We've also observed a difference of 0.013 (SD=0.016) in our other co-primary outcome change in brain activity from hypoglycemia to euglycemia in the striatum between T1DM Aware and Unaware. Thus, for Aim 3 a sample size of 20 T1DM Unaware subjects per arm will provide 80% power to detect a difference of 0.22 in brain glucose and 0.013 in change in brain activity. We will enroll 65 Unaware for Aim 3 in order to accommodate a potential 10% dropout rate.

Aim 1 Analysis: Comparison of brain activity between groups will be performed using a repeated measures mixed model. The outcome will be brain activity in our primary region of interest, the caudate region of the striatum. Fixed factors for group (unaware, aware, HC), glucose category (eugly, mild hypo, moderate hypo) and their interaction will be included. Linear contrasts comparing changes in brain activation from euglycemia to moderate hypo between groups will be estimated and evaluated at the 0.017 Bonferroni corrected significance level. Secondary analyses will examine other promising ROIs (hypothalamus and prefrontal cortex). Similar analyses will be done to assess group differences in resting state connectivity and hormones.

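### Aim 3 sizing has no scan-failure allowance for the Unaware group, the only group scanned twice per modality; with 40 entrants, about 32 usable pairs per outcome remain

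*Combined protocol and SAP*

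**What the plan says.** Section I, item 13 (Statistical Considerations) starts from 25 Aware and 25 control subjects and inflates both: "We will enroll 27 aware and 27 healthy controls to accommodate a potential" "5% inadequate scan rate". For the third group it states "The T1DM Unaware group sample size (n=40) was first determined to provide sufficient power for Aim 3", on the basis of 20 per arm and 80% power, and then "We will enroll 65 Unaware for Aim 3 in order to accommodate a potential 10% dropout rate". No scan-failure rate is mentioned for that group.

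Section I, item 4 (Research Plan) gives 40 Unaware subjects for Aim 1 and the same groups for Aim 2. For Aim 3 it says "T1DM-UA subjects that completed Aims 1 and 2 will participate in Aim 3" and "40 T1DM-UA subjects will be assigned to use a Dexcom G6 continuous monitoring system". Both fMRI and MRS are repeated at 12 weeks. The word for finishing Aims 1 and 2 is not defined, and no image-quality condition is attached to it.

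Item 13 describes an analysis for Aim 1 and one for Aim 2, but none for Aim 3. Its missing-data plan covers reminders, missing items, a missing-at-random assumption and predictors of dropout. It does not mention unusable scans.

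**The concern.** Aim 3 asks whether CGM reverses altered brain metabolism and connectivity, which is a within-subject question. Scoring a change on one outcome takes two usable scans of the same modality. Aware and control subjects are scanned once per modality and receive an allowance for scan failure. Unaware subjects are scanned twice per modality and receive none. The group most exposed to the problem is therefore the one not sized for it.

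At stake is the Aim 3 power statement, which treats 40 Unaware subjects, 20 per arm, as fully evaluable. If 40 is the number entering, the plan's own loss rates mean that fewer can be scored for change.

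**Working it through.** **Inputs from the plan (Section I, items 4 and 13).** 40 Unaware; 20 per arm; 80% power; 10% dropout; 5% inadequate scans; difference 0.013 with SD 0.016 (change in striatal activity); difference 0.22 with SD 0.26 (brain glucose).

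**Assumptions.** Two-sided 0.05, because item 13 gives no level for Aim 3. The 5% applies to each scan, independently of other scans and of dropout; the plan does not state its unit, so a once-per-subject reading is shown as well. The listed SDs apply to the quantity compared.

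**Step 1: the plan's own figures.**
- Aware and controls: 25 / 0.95 = 26.3, so 27. This reproduces.
- Unaware: 40 / 0.90 = 44.4, so 45. The stated 65 does not reproduce; it would imply a loss of 1 − 40/65 = 38%.
- Power at 20 per arm, noncentral t with 2n − 2 degrees of freedom and noncentrality d × √(n/2): d = 0.013/0.016 = 0.8125 gives 70.7%; d = 0.22/0.26 = 0.846 gives 74.1%. The stated 80% is not reached before any loss. An unstated one-sided 0.05 test would give 82.2% and 84.9% (normal approximation).

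**Step 2: usable pairs per outcome from 40 entrants.**
- After dropout: 40 × 0.90 = 36.
- After scan failure at both times: 36 × 0.95² = 32.5. The retained share is 0.90 × 0.9025 = 81.2%, so 18.8% is lost: 10 points dropout and 8.8 points scan failure.
- If the 5% is once per subject: 40 × 0.90 × 0.95 = 34.2, a loss of 14.5%.
- Both co-primaries scorable in the same subject: 40 × 0.90 × 0.95⁴ = 29.3.
- Other starting numbers, per-scan reading: 45 × 0.812 = 36.6; 65 × 0.812 = 52.8.
- Entrants needed for 40 pairs per outcome: 40 / 0.812 = 49.2, so 50; on the once-per-subject reading 40 / 0.855 = 46.8, so 47.

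**Step 3: power on those pairs, two arms, two-sided 0.05, noncentral t.**

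| Evaluable (per arm) | Activity | Brain glucose |
|---|---|---|
| 40 (20), no loss | 70.7% | 74.1% |
| 36 (18), after dropout | 65.8% | 69.4% |
| 32 (16), after dropout and scan failure | 60.4% | 63.9% |
| 52 (26), if 65 enter | 81.9% | 84.9% |

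Scan failure alone costs 65.8 − 60.4 = 5.4 and 69.4 − 63.9 = 5.5 points. With a one-sided 0.05 test (normal approximation), 18 per arm gives 78.6% and 81.4%, and 16 per arm gives 74.3% and 77.3%.

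**Step 4: single-arm paired reading.** Noncentrality is (difference / SD of change) × √n, with n − 1 degrees of freedom. The SD of the before-after change is not given; it is taken between the listed SD and that SD × √2. With 32 pairs, power is 99.4% to 88.3% (activity) and 99.6% to 90.6% (brain glucose).

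**Step 5: would a stricter entry rule help?** If Aim 3 required both baseline modalities to be usable, 40 × 0.95² = 36.1 would enter. After dropout and follow-up scan failure, 36.1 × 0.90 × 0.95 = 30.9 pairs per outcome would remain, against 32.5 under the present rule.

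**The case against.** The strongest reply is that item 13 enrols 65 Unaware subjects. If 65 truly enter, about 53 pairs per outcome remain and there is no shortfall against 40. That stands as a conditional. However, item 13 attributes the 65 to dropout alone, the Research Plan gives 40 Unaware throughout, and item 6 gives 65 as the total of all type 1 subjects (40 + 25). The documents do not settle which is meant, so the 65 cannot be taken as the missing allowance.

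The second reply is that the power loss depends on the design. The Research Plan assigns all 40 to one device, although the repeat-scan paragraph still mentions a second group. As a single-arm paired comparison, 32 pairs would be ample. This also stands; the low power belongs to the two-arm wording, which is the only Aim 3 power statement in the plan.

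Third, a mixed model like those for Aims 1 and 2 could keep subjects with one usable scan under missing at random. That is possible, but no Aim 3 model is written, and such subjects say little about within-person change.

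Two stronger readings are tempting and are not supported. A reader might infer that the missing scan allowance costs 19% of subjects; 10 of those points are dropout that the plan already names. A reader might also infer that the entry sentence deliberately admits subjects without a usable baseline, that they take places from others, and that they should be excluded. The term is merely undefined. With 40 Unaware as the whole group, nobody is displaced. Exclusion lowers the evaluable count (Step 5), because a subject with one failed modality can still be scored on the other co-primary.

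**Conclusion.** The point holds: the Unaware group carries no stated scan-failure allowance for Aim 3, although it needs two usable scans per outcome. With 40 entrants, the plan's rates leave about 32 usable pairs per outcome (34 if the 5% is once per subject), of which scan failure accounts for about 9 percentage points of loss (4.5 on the once-per-subject reading). On the two-arm wording at two-sided 0.05, the stated 80% is not delivered: it is 71% and 74% before losses, 66% and 69% after dropout, and 60% and 64% after both.

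This rests on 40 entering, independent failures and the listed SDs. It does not show that Aim 3 is underpowered in every case: the shortfall disappears with 65 entrants, and a single-arm paired analysis would keep about 88% or more.

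**What to change.** In Section I, item 13:
- Reconcile the 40 and 65 Unaware subjects across items 4, 6 and 13.
- State whether the 5% is per scan or per subject, and apply it to the Unaware group at both time points together with the 10% dropout.
- Restate Aim 3 power for the resulting evaluable pairs, separately for each co-primary outcome, with the significance level, the sidedness and the design actually used (two arms or a single-arm before-after comparison).

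Keep subjects with one failed baseline modality in Aim 3 and count evaluability outcome by outcome.

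The cost is a few sentences and either a lower stated power or more Unaware entrants. Forty pairs per outcome would take about 50 entrants on the per-scan reading, or 47 on the once-per-subject reading. If 65 is confirmed as the Unaware number, no further recruitment is needed to reach 40 pairs, only a statement that the 65 also covers scan failure.
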